9.2.1.1. Suspected Unexpected Serious Adverse Reactions

Suspected unexpected serious adverse reactions (SUSARs) are serious events that are not listed in the IB and that the investigator identifies as related to investigational product or procedure. United States 21 CFR 312.32 and European Union Clinical Trial Directive 2001/20/EC and the associated detailed guidances or national regulatory requirements in participating countries require the reporting of SUSARs. Lilly has procedures that will be followed for the identification, recording and expedited reporting of SUSARs that are consistent with global regulations and the associated detailed guidances.

Patients who have a Grade 3 infusion-related reaction will not receive further treatment with LY3127804 but will continue to be followed per protocol.

Grade 4

- Stop the infusion and disconnect the infusion tubing from the patient.
- Administer diphenhydramine hydrochloride 50 mg IV (or equivalent), dexamethasone 8 to 10 mg IV (or equivalent), and other medications/treatment as medically indicated.
- Give epinephrine or bronchodilators as indicated.

Patients who have a Grade 4 infusion-related reaction will not receive further treatment with LY3127804 but will continue to be followed in the study.

9.2.3. Complaint Handling

Lilly collects product complaints on investigational products and drug delivery systems used in clinical studies in order to ensure the safety of study patients, monitor quality, and to facilitate process and product improvements.

Patients will be instructed to contact the investigator as soon as possible if he or she has a complaint or problem with the study drug so that the situation can be assessed.

9.2.4. Adverse Events of Special Interest – Secondary Infections

Adverse events of special interest for this study including infections in addition to SARS-CoV-2, inclusive of all sites and pathogens. Site of infection, source of culture (e.g. BAL, tracheal aspirate, sputum, blood, urine) and pathogen(s) identified (including fungal and bacterial pathogens) should be recorded.

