- l Pre-dose ECG to be collected within 1 calendar day of study drug administration. Post-dose ECG to be collected within 1 hour of study drug administration.
- m The time from screening to randomization is provided as a guidance and may be modified based on clinical needs.
- n The exact start and end time study drug infusion will be recorded. The time from randomization to study drug administration is provided as a guidance and may be modified based on clinical needs.
- o Range of the average lowest value of the SpO₂ and highest value of O₂ flow rate administered and method of delivery should be recorded.
- p NIAID ordinal scale is provided in Section 9.1.2.1. If IMV/ECMO is initiated or withdrawn, the date and reason for initiation and withdrawal of care (clinical deterioration, lack of clinical response, resource limitation, or other medical decision) should be captured.
- q Any secondary infection in addition to Severe Acute Respiratory Syndrome Corona Virus (SARS-CoV-2) is an Adverse Event of Special Interest (See Section 9.2.4) and the site of infection, the culture source, and the pathogen(s) identified should be captured. Anti-infective therapy initiated (including anti-bacterial and anti-fungal agents) should be captured under Concomitant Medications.
- r Supportive pulmonary care provided should be recorded as specified in the data capture documents. Specifically, proning should be recorded for any treatment day on which the time of maintaining a patient in a prone position is at least 8 hours.
- s Concomitant medications captured should include unapproved ("off-label") medication (for example, chloroquine, hydroxychloroquine, and IL-6 antagonists).

3. Introduction

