9.2. Adverse Events

A clinical trial AE is any untoward medical event associated with the use of a drug or drug delivery system in humans, whether or not it is considered related to that drug or drug delivery system.

Investigators are responsible for monitoring the safety of patients who have entered this study and for alerting the sponsor or its designee to any event that seems unusual, even if this event may be considered an unanticipated benefit to the patient.

The investigator is responsible for the appropriate medical care of patients during the study.

Investigators must document their review of each laboratory safety report and electrocardiogram (ECG).

The investigator remains responsible for following, through an appropriate health care option, AEs that are serious or otherwise medically important, considered related to the investigational product or the study, or that caused the patient to discontinue the study drug before completing the study. The patient should be followed until the event resolves, stabilizes with appropriate diagnostic evaluation, or is reasonably explained. The frequency of follow-up evaluations of the AE is left to the discretion of the investigator.

Lack of drug effect is not an AE in clinical studies, because the purpose of the clinical study is to establish treatment effect.

After the informed consent form (ICF) is signed, study site personnel will record via electronic data capture (EDC) the occurrence and nature of each patient’s pre-existing conditions, including clinically significant signs and symptoms of the disease under treatment in the study. In addition, site personnel will record via eCRF any change in the condition(s) and any new conditions as

AEs. Investigators should record their assessment of the potential relatedness of each AE to protocol procedure or investigational product via EDC.

The investigator will interpret and document whether or not an AE has a reasonable possibility of being related to study treatment, study device, or a study procedure, taking into account the disease, concomitant treatment, and pathologies.

A “reasonable possibility” means that there potentially is a cause and effect relationship between the investigational product, study device, and/or study procedure and the AE.

The investigator will use AE follow-up forms to record additional details regarding AEs related to injection sites and hypersensitivity events.

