9.2.1. Serious Adverse Events

Study-specific clinical outcomes of progressive pulmonary failure in hospitalized patients with presumed or confirmed COVID-19 are exempt from all serious adverse event reporting unless the investigator deems the event to be related to the administration of study drug. Monitoring by the DMC will include continuous assessment of a potential imbalance in aggregate events between the treatment and control groups (please refer to Section 9.4.5).

The following events will be considered clinical outcomes and not reported as SAEs:

- Death related to progressive pulmonary failure and/or ARDS, that is, related to severe ARDS or a sequela of ARDS based on the interpretation of the investigator.
- Cardiovascular events: cardiac failure.
- Respiratory events: pneumonia, hemoptysis, decreased PaO₂/FiO₂, mechanical ventilation/ECMO, hypoxia, hypoxemia, ARDS, acute lung injury, or respiratory failure.
- Systemic inflammatory response syndrome related criteria: tachypnea, hypopnea, leukocytosis, leukopenia, hypothermia, hyperthermia, tachycardia, or bradycardia.
- Secondary infections

An SAE is any AE from this study that results in one of the following outcomes and is not classified as a clinical outcome of COVID-19 using the definitions shown in Section 9.2.:

- death that is not related to COVID-19 or a sequela of COVID-19 or death that is considered by the investigator to be related to study drug
- prolonged inpatient hospitalization or re-hospitalization life-threatening experience (that is, immediate risk of dying)
- persistent or significant disability/incapacity
- congenital anomaly/birth defect

- important medical events that may not be immediately life-threatening or result in death or hospitalization but may jeopardize the patient or may require intervention to prevent one of the other outcomes listed in the definition above.

The study site personnel must alert the sponsor, or its designee, of any SAE as soon as practically possible but no later than 24 hours.

Additionally, study site personnel must alert the sponsor, or its designee, of any SAE within 24 hours of Investigator awareness of the event via a sponsor-approved method. If alerts are issued via telephone, they are to be immediately followed with official notification on study-specific SAE forms. This 24-hour notification requirement refers to the initial SAE information and all follow-up SAE information.

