5.1 List of Tables

	Title
1	Demographics and Baseline Characteristics (Safety Population)
2	Demographics and Baseline Characteristics by Site (Safety Population)
3	Analysis Populations
4	Patient Disposition by Treatment Group and Overall
5	Drug Exposure (Safety Population)
6	Concomitant Medications By Drug Class And Name (Safety Population)
7	Medical History (Safety Population)
8	Overview of Adverse Events (Safety Population)
9	Number and Percentage of Subjects with Treatment Emergent Adverse Events by System Organ Class and Preferred Term (Safety Population)
10	Number and Percentage of Subjects with Study Drug Related Treatment Emergent Adverse Events by System Organ Class and Preferred Term (Safety Population)
11	Number and Percentage of Subjects with Treatment Emergent Adverse Events by System Organ Class, Preferred Term, and Maximal Severity (Safety Population)
12	Serious Treatment Emergent Adverse Events by System Organ Class and Preferred Term (Safety Population)
13	Treatment Emergent Adverse Events Leading to Study Drug Discontinuation by System Organ Class and Preferred Term (Safety Population)
14	Treatment Emergent Adverse Events that Result in Death by System Organ Class and Preferred Term (Safety Population)
15	Hematology Lab Results by Study Day and Change from Baseline (Safety Population)
16	Chemistry Lab Results by Study Day and Change From Baseline (Safety Population)
17	Hematology Shift from Baseline (Safety Population)
18	Chemistry Labs Shift from Baseline (Safety Population)
19	Subjects with Abnormal Hematology Results (Safety Population)
20	Subjects with Abnormal Chemistry Results (Safety Population)
21	Pregnancy Status (Safety Population)
22	Vital Signs and Change from Baseline by Study Day (Safety Population)
23	Subjects with Extreme Vital Signs (Safety Population)

24	Number and Percentage of Subjects with Abnormal ECGs (Safety Population)
25	COVID-19, Influenza, RSV, and Respiratory Viral Panels (Safety Population)
26	(Primary Objective) Ventilator Free Days (Efficacy Population)
27	Ventilator Free Days by SARS-Cov-2 Status (Efficacy Population)
28	Ventilator Free Days by Age Group (Efficacy Population)
29	Ventilator Free Days by Sex (Efficacy Population)
30	Ventilator Free Days by BMI Group (Efficacy Population)
31	Ventilator Free Days by Number Of Doses (Efficacy Population)
32	Ventilator Free Days by NIAID = 2 within Day 4 (Efficacy Population)
33	Ventilator Free Days by NIAID = 3 vs. NIAID = 4 or 5 (Efficacy Population)

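### Secondary infections are the only adverse event of special interest the protocol names, but no planned output counts the patients affected in each arm

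*Protocol*

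**What the plan says.** - Protocol 9.2.4 defines the event of special interest: "Adverse events of special interest for this study including infections in addition to SARS-CoV-2, inclusive of all sites and pathogens". Footnote q to the Schedule of Activities repeats it: "Any secondary infection in addition to Severe Acute Respiratory Syndrome Corona Virus (SARS-CoV-2) is an Adverse Event of Special Interest". Both ask sites to capture the site of infection, the culture source and the pathogen. No other event of special interest is named, although the word *including* leaves the list formally open.
- Protocol 9.2.1 introduces a list with "The following events will be considered clinical outcomes and not reported as SAEs", and one bullet is "Secondary infections". The exemption is lifted if the investigator judges the event related to study drug. A separate bullet begins "Respiratory events: pneumonia, hemoptysis".
- Protocol 9.2 has sites record worsening as well as new events: "site personnel will record via eCRF any change in the condition(s) and any new conditions as" AEs.
- SAP 4.13.2 summarises treatment-emergent events by system organ class and preferred term. A patient counts once per class, but once for every different preferred term within it. The matching entry in SAP 5.1 is Table 9, "Number and Percentage of Subjects with Treatment Emergent Adverse Events by System Organ Class and Preferred Term (Safety Population"). Table 11 adds maximal severity.
- SAP 4.1 sets the convention for dichotomous comparisons: difference in proportions with a 90% Wald interval.

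**The concern.** An event is named as being of special interest so that the report can say how often it occurred in each arm. Here the protocol goes to the trouble of collecting infection detail, then removes most of these events from serious-event reporting, and the SAP never brings them back together. If the SAP is followed exactly, the report will show many infection terms in separate small rows and one class total. It will not show the number of patients per arm with a secondary infection.

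What is at stake is the readability of the one safety signal the protocol singles out. A moderate excess spread over many sites and pathogens may not stand out in any single row. The class total is a safe substitute only if it contains little else.

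**Working it through.** **1. Search for a grouped output.** SAP 4.13.2 plans summaries of treatment-emergent, serious, fatal, discontinuation-related, drug-related and maximal-severity events. SAP 5.1 to 5.3 list 43 tables, 29 listings and 5 figures. None names secondary infections or events of special interest. The nearest are Tables 9, 10 and 11 (by class and term), Table 12 (serious), Table 14 (fatal), Table 25 (COVID-19 and viral panels) and Listing 8 (all adverse events). No planned table summarises the infection-site, culture-source or pathogen data.

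**2. Can the patient count be rebuilt from the printed tables?** Not in general. A patient with a bloodstream and a urinary infection adds one to each of two preferred-term rows. The number affected therefore lies somewhere between the largest single row and the sum of the rows. The class total removes the double counting, but no rule excludes COVID-19 terms from it.

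**3. Does the serious-event table help?** Only for serious infections judged drug-related. The rest are exempt under Protocol 9.2.1.

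**4. Could the class total mislead?** The documents give no infection rate, so there is no planned figure to reproduce. The following is conditional on worsening COVID-19 pneumonia being recorded as treatment-emergent and coded to the same class.

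Inputs:
- *s*, secondary-infection rate: assumed.
- *c*, COVID-19 pneumonia event rate: assumed. The planned ventilation rates in Protocol 10.1 serve as a proxy: 25% on placebo and, with the 50% improvement, 12.5% on LY3127804.
- n = 105 per arm (Protocol 10.1).

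Under independence, class total = 1 − (1 − s)(1 − c).

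| s, placebo vs drug | c, placebo vs drug | Class total, placebo vs drug | Difference |
|---|---|---|---|
| 10% vs 20% | 0 vs 0 | 10.0% vs 20.0% | +10.0 points |
| 10% vs 20% | 25% vs 25% | 1−0.90×0.75 = 32.5% vs 1−0.80×0.75 = 40.0% | +7.5 |
| 10% vs 20% | 25% vs 12.5% | 32.5% vs 1−0.80×0.875 = 30.0% | −2.5 |
| 5% vs 10% | 25% vs 12.5% | 1−0.95×0.75 = 28.75% vs 1−0.90×0.875 = 21.25% | −7.5 |
| 15% vs 30% | 25% vs 12.5% | 1−0.85×0.75 = 36.25% vs 1−0.70×0.875 = 38.75% | +2.5 |

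For the third row, other overlap assumptions give the same sign. If the two events never coincide, the totals are 35.0% vs 32.5% (−2.5). If the rarer event is nested in the commoner, they are 25.0% vs 20.0% (−5.0).

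Break-even for 10% vs 20% with c = 25% on placebo: 0.80 × (1 − c on drug) = 0.90 × 0.75 = 0.675, so c on drug = 15.6%, a 37.5% relative reduction. With c = 10% on placebo, 0.80 × (1 − c on drug) = 0.81 has no solution at or above zero, so no reduction can cancel the excess.

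**5. What a dedicated row would show.** At 10% vs 20%, SE = √[(0.10×0.90 + 0.20×0.80)/105] = 0.0488. The 90% Wald interval is 10.0 ± 1.645 × 4.88, about +2.0 to +18.0 points. For the class total of 32.5% vs 30.0%, SE = √[(0.325×0.675 + 0.30×0.70)/105] = 0.0639 and the interval is about −13.0 to +8.0.

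One-sided 0.05 power, Φ[(d − 1.645·SE₀)/SE₁] with SE₀ pooled and SE₁ unpooled, is about 65% for the dedicated row at 10% vs 20%. It is 30% for the class total when c is 25% in both arms. At 15% vs 30% it falls from 83% to 10% when c is 25% vs 12.5%. These powers only gauge dilution; the plan sets no formal safety test.

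**The case against.** The strongest reply is that little is actually lost. Every infection term has a by-arm row in Table 9 and a severity breakdown in Table 11, drug-related ones enter Table 10, fatal ones Table 14, and all are in Listing 8. Protocol 10.3.1 and SAP 4.1 allow further exploratory analyses. Protocol 10.3.4 promises no table of events of special interest, so the SAP breaks no explicit commitment. All of this stands. A reader might infer that secondary infections are not tabulated by arm at all, or that the count could never be obtained; neither is right. What is missing is a pre-specified patient-level count. One produced after the fact would need the excluded terms chosen once results are known.

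The second reply concerns masking, and it largely stands. The documents do not say how worsening COVID-19 pneumonia is coded. Protocol 9.2.1 places pneumonia among respiratory events, apart from secondary infections. Every patient enters with pneumonia, and SAP 4.13.2 counts a term already present only if it worsens beyond its maximum severity in screening. Ventilation is only a proxy for a pneumonia event. Preferred-term rows would also show a fall in pneumonia terms separately.

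Third, Protocol 9.2.1 says "Monitoring by the DMC will include continuous assessment of a potential imbalance in aggregate events between the treatment and control groups". That is monitoring during the trial, with details left to a charter outside these documents. It does not supply the final by-arm count.

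**Conclusion.** The gap is real and rests on the documents alone: the one named event of special interest has no grouped by-arm output, preferred-term rows cannot be summed to patients, the class total has no stated exclusion of COVID-19 terms, and the serious-event table will largely, though not wholly, miss these events.

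A reader might go further and infer that the class total does mix secondary infections with COVID-19 pneumonia and will show a harm as a benefit. The documents do not support that. Reversal needs an unstated coding assumption, assumed infection rates, and ventilation rates standing in for pneumonia events. Within those assumptions the effect ranges from none (no pneumonia events) through dilution (+10.0 to +7.5 points) to reversal (+10.0 to −2.5); at 15% vs 30% the excess shrinks to +2.5 points without changing sign. The case for the added table does not depend on masking.

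**What to change.** Add to SAP 4.13.2 and 5.1 one table, on the Safety Analysis Set, of patients with at least one treatment-emergent secondary infection by arm, with SARS-CoV-2 and COVID-19 terms excluded. Report the difference in proportions with a 90% interval, in line with SAP 4.1. Add to SAP 5.2 one listing showing site of infection, culture source, pathogen and grade. State the term-exclusion rule in the SAP and settle it blind to treatment arm.

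The cost is one table, one listing and a short rule, all from data the protocol already collects. Further breakdowns by site, pathogen or grade are optional.

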9.3. Treatment of Overdose

There is no antidote to LY3127804. In case of overdose, use supportive measures.

9.4. Safety**9.4.1. Electrocardiograms**

For each patient, ECGs should be collected according to the Schedule of Activities (Section 2).

Any clinically significant findings from ECGs that result in a diagnosis and that occur after the patient receives the first dose of the investigational treatment should be reported to Lilly or its designee as an AE via EDC.

9.4.2. Vital Signs

For each patient, vital sign measurements should be conducted according to the Schedule of Activities (Section 2).

The sponsor recognizes that vital sign assessments will be performed more frequently than indicated in the Schedule of Events, with continuous monitoring in the ICU and every 2 to 4 hours in non-ICU settings. The time points specified in the protocol are collection times used for data analysis purposes only. The vital sign schedule in the protocol is not intended to interfere with standard of care practices in a given hospital unit. In all cases, institutional standard of care with respect to monitoring of patients is allowed and encouraged.

Any clinically significant findings from vital sign measurements that result in a diagnosis and that occur after the patient receives the first dose of study treatment should be reported to Lilly or its designee as an AE via EDC.

9.4.3. Laboratory Tests

For each patient, laboratory tests detailed in ([Appendix 2](#)) should be conducted according to the Schedule of Activities (Section 2).

Any clinically significant findings from laboratory tests that result in a diagnosis and that occur after the patient receives the first dose of investigational product should be reported to Lilly or its designee as an AE via EDC.

9.4.4. Immunogenicity Assessments

Results from Clinical Study JQBA are consistent with a low risk for the development of significant levels of anti-drug antibodies. The proposed treatment will include one or two doses of LY3127804, making the mounting of a significant specific immune response to LY3127804 unlikely. Additionally, the collection of multiple blood draws presents significant challenges and an additional risk of infection to site personnel and is deemed unfeasible. There will be no assessment of immunogenicity as part of Study UDAA.

9.4.5. Safety Monitoring

The study will have a Data Monitoring Committee (DMC) consisting of at least 2 physicians and one statistician, all experienced clinical trialists and external to the sponsor. The role of the DMC is to advise the sponsor regarding conduct of the study. Only the DMC is authorized to evaluate unblinded data. Study sites will receive unblinded results ONLY if they need to know for the safety of their patients. Unblinding details are specified in the unblinding plan section of the statistical analysis plan (SAP) or a separate unblinding plan document.

In the event that safety monitoring uncovers an issue that needs to be addressed by unblinding at the group level, only members of the DMC can conduct additional analyses of the safety data.

All deaths and SAE reports will be reviewed in a blinded manner by Lilly during the clinical trial. These reports will be reviewed to assure completeness and accuracy but will not be unblinded to Lilly during the clinical trial. If a death or clinical AE is deemed serious, unexpected, and possibly related to investigational product, one individual (or designee) in Lilly Global Patient Safety will be unblinded for regulatory reporting and safety monitoring purposes. These measures will preserve the integrity of the data collected during this trial and minimize any potential for bias while providing for appropriate safety monitoring.

9.5. Pharmacokinetics

Samples for pharmacokinetic analysis will not be collected in this study.

